L8. Hypokalaemia (mg/dl)***	-	3.0 – 3.4	2.5 – 2.9
			> 3.0; or Hgb < 7.0
			< 1.0
			< 0.5
			< 0.5
			< 20; recurrent platelet transfusions required
			> 13.5; or associated coma
			> 500, or associated with ketoacidosis
			> 7.0 or any arrhythmia
			< 6.5 or occurrence of tetany
			< 30 or coma
			< 120
			< 2.5

L. Chemistry (Continued)

L9. CPK (also if polymyositis-disease) ****	> ULN – 1.5 × ULN	> 2.5 – 5.0 × ULN	> 5.0 – 10.0 × ULN	> 10.0 × ULN
L10. Serum uric acid	1.2 – 1.6 × ULN	1.7 – 2.9 × ULN	3.0 – 5.0 × ULN or gout	NA
L11. Creatinine (mg/dl) ***	> 1 – 1.5 × Baseline; > ULN – 1.5 × ULN	> 1.5 – 3.0 × Baseline; > 1.5 – 3.0 × ULN	> 3.0 baseline; > 3.0 – 6.0 × ULN	> 6.0 × ULN
L12. SGOT (AST)	1.2 – 1.5 × ULN	1.6 – 3.0 × ULN	3.1 – 8.0 × ULN	> 8.0 × ULN
L13. SGPT (ALT)	1.2 – 1.5 × ULN	1.6 – 3.0 × ULN	3.0 – 8.0 × ULN	> 8.0 × ULN
L14. Alkaline phosphatase	1.1 – 1.5** × ULN	1.6 – 3.0 × ULN	3.0 – 5.0 × ULN	> 5.0 × ULN
L15. T. bilirubin	1.1 – 1.4 × ULN	1.5 – 1.9 × ULN	2.0 – 3.0 × ULN	> 3.0 × ULN
L16. LDH	1.3 – 2.4 × ULN	2.5 – 5.0 × ULN	5.1 – 10 × ULN	> 10 × ULN
M. Urinalysis				
M1. Haematuria	Micro only	Gross, no clots	Clots, transfusion < 2 units	Transfusion required
M2. Proteinuria (per 24 h)	300 – 500 mg (tr/1+)	501 – 1999 mg (2+)	2 – 5.0 g (3+) nephrotic syndrome	5.0 g (4+) anasarca
M3. WBC in urine	NA	NA	Indicating acute interstitial nephritis	Associated with acute renal failure
M4. Uric acid crystals	Present without symptoms	NA	With stones or symptoms of stones (e.g., renal colic)	Causing renal outflow obstruction and hospitalization

*: in L11, 1.5 – 1.8 × ULN is changed to 1.4 – 1.8 × ULN.

**: in L14, 1.1 – 2.0 × ULN is changed to 1.1 – 1.5 × ULN.

***: in L3, L7 and L8, mg/dl is changed to mmol/l

****: NCI CTC grade

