- Absolute neutrophil count (ANC) < 1,500/ $\mu$ L
- Platelet count < 100,000 / $\mu$ L
- Absolute lymphocyte count < 800/ $\mu$ L
- Hemoglobin < 10 g/dL

22. History of any of the following cardiovascular conditions:

- Moderate to severe congestive heart failure (New York Heart Association class III or IV);
- Recent (within past 6 months) cerebrovascular accident, myocardial infarction, coronary stenting;
- Uncontrolled hypertension as defined by a persistent confirmed systolic blood pressure > 160 mmHg or diastolic blood pressure > 100 mmHg;
- Any other condition which, in the opinion of the Investigator, would put the subject at risk by participating in the protocol.

23. Positive result of beta-D-glucan or two consecutive indeterminate results of beta-D-glucan.

24. Subject with any planned (elective) surgery within the first 12 weeks of the study.

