**Table 7. Specific Toxicity Management Guidelines for Abnormal Laboratory Values**

Laboratory Parameter	Toxicity Management Guideline
Hemoglobin	

• If hemoglobin < 8 g/dL, interrupt study drug dosing and confirm by repeat testing with new sample.

• If hemoglobin decreases <math>\geq 3.0</math> g/dL from baseline without an alternative etiology, interrupt study drug dosing and confirm by repeat testing with new sample.

• If hemoglobin decreases <math>\geq 3.0</math> g/dL from baseline and an alternative etiology is known, the subject may remain on study drug at the investigator's discretion.

• If confirmed, continue to withhold study drug until hemoglobin value returns to normal reference range or its baseline value.

Absolute neutrophil count (ANC)	

• If confirmed < 1000 cells/<math>\mu</math>L by repeat testing with new sample, interrupt study drug dosing until ANC value returns to normal reference range or its baseline value.

• Discontinue study drug if confirmed < 500 cells/<math>\mu</math>L by repeat testing with new sample.

Absolute lymphocyte counts (ALC)	

• If confirmed < 500 cells/<math>\mu</math>L by repeat testing with new sample, interrupt study drug dosing until ALC returns to normal reference range or its baseline value.

Total white blood cell count	

• If confirmed < 2000 cells/<math>\mu</math>L by repeat testing with new sample, interrupt study drug dosing until white blood cell count returns to normal reference range or its baseline value.

Platelet count	

• If confirmed < 50,000 cells/<math>\mu</math>L by repeat testing with new sample, interrupt study drug dosing until platelet count returns to normal reference range or its baseline value.

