J4. Pleuritic pain (pleurisy)	Transient, intermittent symptoms, no treatment or OTC meds relieve	Persistent symptoms, requires prescription meds for relief	Prolonged symptoms, interferes with function, requires frequent narcotic pain relief	Debilitation, requiring hospitalisation
J5. Pneumonitis (pulmonary infiltrates)	Asymptomatic radiographic changes, transient, no treatment required	Symptomatic, persistent, requiring corticosteroids	Symptomatic, requiring treatment including O 2	Debilitating, not reversible; or requiring assisted ventilation
J6. Pulmonary function decreased (FVC or carbon monoxide diffusion capacity – DLCO)	76% – 90% of pre-treatment value	51% – 75% of pre-treatment value	26% – 50% of pre-treatment value	≤ 25% of pre-treatment value

Laboratory Data				
K. Haematology				
K1. Hgb (g/dl) decrease from pre-treatment	1.0 – 1.4	1.5 – 2.0	2.1 – 2.9, or Hgb < 8.0, > 7.0	≥ 3.0, or Hgb < 7.0
K2. Leukopenia (total WBC) × 1000	3.0 – 3.9	2.0 – 2.9	1.0 – 1.9	< 1.0
K3. Neutropenia (× 1000)	1.5 – 1.9	1.0 – 1.4	0.5 – 0.9	< 0.5
K4. Lymphopenia (× 1000)	1.5 – 1.9	1.0 – 1.4	0.5 – 0.9	< 0.5
K5. Platelets (× 1000)	75 – LLN	50 – 74.9	20 – 49.9; platelet transfusion required	< 20; recurrent platelet transfusions
L. Chemistry				
L1. Hypocalcaemia (mg/dl)	1.1 × ULN – 11.5	11.6 – 12.5	12.6 – 13.5; or symptoms present	> 13.5; or associated coma
L2. Hyperglycemia (mg/dl) Fasting	140 – 160	161 – 250	251 – 500	> 500; or associated with ketoacidosis
L3. Hyperkalaemia (mg/dl)	5.5 – 5.9	6.0 – 6.4	6.5 – 7.0 or any ECG change	> 7.0 or any arrhythmia
L5. Hypocalcaemia (mg/dl)	0.9 × LLN – 7.8	7.7 – 7.0	6.9 – 6.5; or associated with symptoms	< 6.5 or occurrence of tetany
L6. Hypoglycemia (mg/dl)	55 – 64 (no symptoms)	40 – 54 (or symptoms present)	30 – 39 (symptoms impair function)	< 30 or coma
L7. Hyponatraemia (mg/dl)	--	125 – 129	120 – 124	< 120
L8. Hypokalaemia (mg/dl)	--	3.0 – 3.4	2.5 – 2.9	< 2.5

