10.3.2.2 Assessment of Shift from Baseline in Clinical Laboratory Variables

The baseline and post-baseline laboratory observations will be categorized as Grade 1, Grade 2, Grade 3, and Grade 4 according to OMERACT criteria (Rheumatology Common Toxicity Criteria v.2.0). For creatine phosphokinase, creatinine, NCI CTC criteria will be used.

For each laboratory variable, shift tables will be generated that cross tabulate the subjects' as deemed appropriate by "as treated" treatment group:

- Category of the baseline value versus category of the final value,
- Category of the baseline value versus maximum category.
- Category of the baseline value versus minimum category.

Note that the minimum/maximum category is used, rather than the category of the minimum/maximum value. The two may be different due to variation in the reference range.

No statistical tests will be performed for this analysis.

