10.3.2.3 Assessment of Potentially Clinical Significant Laboratory Variables

The criteria for potentially clinically significant laboratory values will be determined by OMERACT criteria of Grade 3 or 4. For creatine phosphokinase, creatinine, NCI CTC criteria will be used.

The number and percentage of subjects meeting the criteria for potentially clinically significant laboratory values will be summarized by "as treated" treatment group and overall. Comparisons of the percentage of subjects experiencing a value meeting the criteria between treatment groups will be performed using Fisher's exact tests. Only p-values ≤ 0.100 when rounded to three digits will be presented.

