111. Vertigo (dizziness)	Subjective symptoms, transient, intermittent, no treatment	Objective findings, recurrent, meds relieve, occasionally interfering with function	Persistent, prolonged, interfering with daily function; partial response to medication
J. Pulmonary			
J1. Asthma	Occasional wheeze, no interference with activities	Wheezing, requires oral meds, occasional interference with function	Debilitating, requires nasal O ₂
J2. Cough	Transient, intermittent, occasional OTC meds relieve	Persistent, requires narcotic or other prescription meds for relief	Recurrent, persistent coughing spasms without consistent relief by meds, interferes with function
J3. Dyspnea	Subjective, transient, no interference with function	Symptomatic, intermittent or recurring, interferes with exertional activities	Symptomatic during daily routine activities, interferes with function, treatment with intermittent nasal O ₂ relieves
J4. Pleuritic pain (pleurisy)	Transient, intermittent symptoms, no treatment or OTC meds relieve	Persistent symptoms, requires prescription meds for relief	Prolonged symptoms, interferes with function, requires frequent narcotic pain relief
J5. Pneumonitis (pulmonary infiltrates)	Asymptomatic radiographic changes, transient, no treatment required	Symptomatic, persistent, requiring corticosteroids	Symptomatic, requiring treatment including O ₂
J6. Pulmonary function decreased (FVC or carbon monoxide diffusion capacity – DLCO)	76% – 90% of pre-treatment value	51% – 75% of pre-treatment value	26% – 50% of pre-treatment value $\leq 25\%$ of pre-treatment value

Laboratory Data			
K. Haematology			
K1. Hgb (g/dl) decrease from pre treatment	1.0 – 1.4	1.5 – 2.0	2.1 – 2.9, or Hgb < 8.0, > 7.0
K2. Leukopenia (total WBC) × 1000	3.0 – 3.9	2.0 – 2.9	1.0 – 1.9
K3. Neutropenia (× 1000)	1.5 – 1.9	1.0 – 1.4	0.5 – 0.9
K4. Lymphopenia (× 1000)	1.5 – 1.9	1.0 – 1.4	0.5 – 0.9
K5. Platelets (× 1000)	75 – LLN	50 – 74.9	20 – 49.9; platelet transfusion required
L. Chemistry			
L1. Hypercalcaemia (mg/dl)	1.1 × ULN – 11.5	11.6 – 12.5	12.6 – 13.5; or symptoms present
L2. Hyperglycemia (mg/dl) Fasting	140 – 160	161 – 250	251 – 500
L3. Hyperkalaemia (mmol/l)***	5.5 – 5.9	6.0 – 6.4	6.5 – 7.0 or any ECG change
L5. Hypocalcaemia (mg/dl)	0.9 × LLN – 7.8	7.7 – 7.0	6.9 – 6.5; or associated with symptoms
L6. Hypoglycemia (mg/dl)	55 – 64 (no symptoms)	40 – 54 (or symptoms present)	30 – 39 (symptoms impair function)
L7. Hyponatraemia (mmol/l)***	-	125 – 129	120 – 124

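### SAP Appendix A prints hemoglobin Grade 4 as a fall > 3.0 g/dL where protocol Appendix N has ≥ 3.0, so a fall of exactly 3.0 g/dL has no fall-based grade in the SAP

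*SAP*

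**What the plan says.** SAP Appendix A and protocol Appendix N both reproduce the Rheumatology Common Toxicity Criteria v2.0. For hemoglobin (row K1) they share Grade 3, "2.1 – 2.9, or Hgb < 8.0, > 7.0". For Grade 4 the SAP has "> 3.0; or Hgb < 7.0" and the protocol has "≥ 3.0, or Hgb < 7.0".

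The grades feed several outputs:

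- **Counts and tests.** SAP Section 10.3.2.3 says: "The criteria for potentially clinically significant laboratory values will be determined by OMERACT criteria of Grade 3 or 4". Subjects meeting this are counted by treatment group and compared with Fisher's exact tests.
- **Shift tables.** SAP Section 10.3.2.2 says: "The baseline and post-baseline laboratory observations will be categorized as Grade 1, Grade 2, Grade 3, and Grade 4 according to OMERACT criteria".
- **Long-term data.** SAP Section 10.3.3.2 counts potentially clinically significant values and lists subjects with Grade 3 or 4 results.

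Protocol Section 8.1.5.3 also commits to grading laboratory data by these criteria. The footnotes to SAP Appendix A declare changes to L3, L7, L8, L11 and L14, and flag the NCI CTC grades. They do not mention K1.

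Protocol Table 7 also uses a fall of 3.0 g/dL or more, inclusive, as its hemoglobin-decrease threshold. It calls for interruption only where there is no alternative etiology. Where "an alternative etiology is known, the subject may remain on study drug at the investigator's discretion".

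**The concern.** A grading scale should give each fall in the graded range exactly one grade. The protocol's scale has no gap at 3.0 g/dL, and the SAP's does. On a 0.1 g/dL scale, 3.0 is an ordinary reportable value. A subject could therefore meet the protocol's hemoglobin-decrease threshold and be Grade 4 in the protocol's table, yet have no grade in the analysis.

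The mismatch acts in one direction only, towards a lower grade. Hemoglobin matters here because the protocol's introduction expects upadacitinib to work without causing excessive anemia. Grade 3/4 counts are also likely to be small, so one misgraded subject can visibly change an arm's figure.

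**Working it through.** The plan states no figure to reproduce, so the check compares the two tables directly.

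**1. Does the cell belong to K1?** In the SAP text as read from the PDF, the Grade 4 entries are separated from their rows and listed together after L8. There are 12 entries for 12 rows (K1–K5, L1–L3, L5–L8). Taken in order, they match those rows, and the first falls on K1.

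**2. Where do the tables differ?** Both K1 scales were coded on a 0.1 g/dL grid, with baseline from 10.0 to 17.0 g/dL and on-treatment value from 5.0 g/dL up to baseline. The lower baseline limit reflects the screening exclusion "Hemoglobin < 10 g/dL" (protocol Section 5.2.2). The scales disagree at 71 grid pairs, all with a fall of exactly 3.0 g/dL. Baselines below 10.0 were checked separately.

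| Baseline (g/dL) | Value after a 3.0 fall | SAP grade | Protocol grade |
|---|---|---|---|
| below 10.0 | below 7.0 | 4 | 4 |
| exactly 10.0 | 7.0 | none | 4 |
| 10.1–10.9 | 7.1–7.9 | 3 (absolute criterion) | 4 |
| 11.0 or more | 8.0 or more | none | 4 |

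Of the 71 pairs, 62 have no SAP grade and 9 are Grade 3. These are grid counts, not patient frequencies. A baseline of exactly 10.0 is ungraded because 7.0 is neither above nor below 7.0, so neither absolute criterion applies.

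**3. How large is the effect?** The documents give no hemoglobin distribution, so this step rests on assumptions. Let X be a subject's largest fall, normal with mean 0.3–1.0 and SD 0.8–1.2 g/dL, reported to 0.1 g/dL. The SAP pools Grades 3 and 4, so the relevant denominator is falls of 2.1 g/dL or more:

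share = P(2.95 ≤ X < 3.05) / P(X ≥ 2.05); expected subjects = 192 × P(2.95 ≤ X < 3.05)

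| Mean, SD | P(exactly 3.0) | P(≥ 2.1) | Share | Expected of 192 |
|---|---|---|---|---|
| 0.3, 0.8 | 0.00017 | 0.0144 | 1.2% | 0.03 |
| 0.3, 1.2 | 0.00265 | 0.0724 | 3.7% | 0.5 |
| 1.0, 0.8 | 0.00220 | 0.0947 | 2.3% | 0.4 |
| 1.0, 1.2 | 0.00829 | 0.1908 | 4.3% | 1.6 |

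Under these assumptions the figures are upper bounds on subjects lost from the count. They ignore baselines of 10.1–10.9, which are still counted as Grade 3. They also ignore any other visit with a Grade 3 value. SAP Table 5 has four post-baseline laboratory windows in Period 1 (Weeks 2, 4, 8 and 12).

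**4. What does the change do?** With ≥ 3.0 in the SAP, every fall of exactly 3.0 g/dL becomes Grade 4, and no other fall changes grade.

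**The case against.** The strongest objection is that this is one character in a badly extracted table. Nearby text has character-level faults, and the Grade 4 column is displaced. The footnotes are also an imperfect record of changes: L8 still prints mg/dl, and the scale printed for L11 is not the one its footnote describes. This stands as a reason to confirm the sign in the PDF. It does not remove the point, because ≥ survives elsewhere in the same appendix (for example in the fever row, C2) and the cell is legible.

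The rest of the objection concerns stronger readings that a reader might infer. The documents do not support them:

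- **Every fall of exactly 3.0 g/dL goes uncounted.** It does not. Values of 7.1–7.9 g/dL are still Grade 3, and values below 7.0 are Grade 4.
- **Anyone with such a fall is missing from the Grade 3/4 count.** The count is per subject and the shift tables use the maximum category. Any other value 2.1–2.9 g/dL below baseline keeps the subject in as Grade 3, and any larger fall as Grade 4. Table 7 also asks for repeat testing where it calls for interruption.
- **Such a fall always triggers interruption.** Table 7 makes this conditional on there being no alternative etiology.
- **Anemia adverse events of special interest are undercounted.** SAP Table 13 identifies them by a MedDRA query on adverse events, not by laboratory grade.
- **A sixth to a third of the relevant events are lost.** Dividing by falls of 3.0 g/dL or more gives 16–37% under the same assumptions, but no planned Grade 3/4 output uses that denominator.

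**Conclusion.** The inconsistency is real, provided that the PDF confirms the sign. The SAP's K1 scale has a gap at exactly 3.0 g/dL that the protocol's scale does not have, and the SAP does not declare it as a change. For baselines of 11.0 g/dL or more, or exactly 10.0, a protocol Grade 4 becomes ungraded. For 10.1–10.9 it becomes Grade 3.

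The practical effect on the pooled Grade 3/4 counts, Fisher tests and listing is small. It is about 1–4% of falls of 2.1 g/dL or more, and at most about 0.03–1.6 of 192 subjects across all arms. Those figures rest on the assumed normal distribution and 0.1 g/dL reporting. The shift tables can also understate the grade of a subject who remains in the Grade 3/4 count. The mean-change and mean-percentage-change analyses of hemoglobin keep the value and are not affected. This is a minor correction, worth making because the effect is one-sided and the remedy is almost free.

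**What to change.** Confirm the sign in the source PDF. If it is as read, change SAP Appendix A K1 Grade 4 to "≥ 3.0, or Hgb < 7.0", as in protocol Appendix N, and make the same change in the grading program. Add a program check that every hemoglobin decrement in the graded range maps to exactly one grade after conversion to SI units, which SAP Section 10.3.1 uses for reporting (3.0 g/dL × 10 = 30 g/L).

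The cost is one character in the SAP and one in the program, plus a short test. The change affects analysis grading only and leaves every clinical-management rule as it is.

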### **6.1.1.3 Adverse Events of Special Interest**

The following AEs of special interest will be monitored during the study (see detailed toxicity management in Section [6.1.7](#)):

- Serious infections
- Opportunistic infections
- Herpes zoster
- Tuberculosis;
- Malignancy (all types);
- Gastrointestinal perforations;
- Adjudicated cardiovascular events (e.g., major adverse cardiovascular event [MACE]);
- Lipid profile changes;
- Anemia;
- Neutropenia;
- Lymphopenia;
- Increased serum creatinine and renal dysfunction;
- Hepatic events and increased hepatic transaminases;
- Elevated creatine phosphokinase (CPK);
- Embolic and thrombotic events (non-cardiac, non-CNS).

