**M. Urinalysis**

M1. Haematuria	Micro only	Gross, no clots	Clots, transfusion < 2 units	Transfusion required
M2. Proteinuria (per 24 h)	300 – 500 mg (tr/1+)	501 – 1999 mg (2+)	2 – 5.0 g (3+) nephrotic syndrome	5.0 g (4+) anasarca
M3. WBC in urine	NA	NA	Indicating acute interstitial nephritis	Associated with acute renal failure
M4. Uric acid crystals	Present without symptoms	NA	With stones or symptoms of stones (e.g., renal colic)	Causing renal outflow obstruction and hospitalization

OTC = over-the-counter medication; ADL = activities of daily living; IV = intravenous; ECG = electrocardiogram; CHF = congestive heart failure; MRI = magnetic resonance imaging; Hb = haemoglobin; LLN = lower limit of normal; ULN = upper limit of normal; WBC = white blood cells; SLE = systemic lupus erythematosus; ANA = antinuclear antibodies; H-2 blockers = histamine-2 blockers; FVC = forced vital capacity

\* For CPK and Creatinine NCI CTC grading will be used. For CPK therefore the following gradings apply: Grade 1: > ULN – 2.5 × ULN; Grade 2: > 2.5 – 5.0 × ULN; Grade 3: > 5.0 – 10.0 × ULN; Grade 4: > 10.0 × ULN; For Creatinine the following gradings apply: Grade 1: > 1 – 1.5 × Baseline; > ULN – 1.5 × ULN; Grade 2: > 1.5 – 3.0 × Baseline; > 1.5 – 3.0 × ULN; Grade 3: > 3.0 baseline; > 3.0 – 6.0 × ULN; Grade4: > 6.0 × ULN

---

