5.2 Analysis Windows

Definition of Study Days (Days Relative to the First Dose of Study Drug)

Study Days are calculated for each collection date relative to the date of the first dose of study drug. It is defined as the number of days between the date of the first dose of study drug and the collection date. Study days are negative values when the collection date of interest is prior to the first study drug dose date. Study days are positive values when the collection date of interest is on or after the first study drug dose date. The day of the

first dose of study drug is defined as Study Day 1, while the day prior to the first study drug dose is defined as Study Day –1 (there is no Study Day 0). Study days are used to map actual study visits to the protocol-specified study visits.

Definition of Analysis Windows

The following rules will be applied to assign actual subject visits to protocol-specified visits. For each protocol-specified study visit, a target study day will be identified to represent the corresponding visit along with a window around the target day. Windows will be selected in a non-overlapping fashion so that a collection date does not fall into multiple visit windows. If a subject has two or more actual visits in one visit window, the visit closest to the target day will be used for analysis. If two visits are equidistant from the target day, then the later visit will be used for analysis.

The visit window and the target study day for each protocol-specified visit in Period 1 are displayed in [Table 4](#) and [Table 6](#) (depending on the different visit schedules of different endpoints). Visit windows for protocol-specified visits in Period 2 are defined similarly.

Table 4. Analysis Windows for Efficacy Analysis for Period 1 (for ACR Components and Morning Stiffness)

Protocol Specified Visit Week	Lower Bound	Target Day	Upper Bound
Baseline	–99	1 ^a	1
1	2	8	11
2	12	15	22
4	23	29	43
8	44	57	71
12	72	85	min (99, first dose date of Period 2)

a. Day of first dose of study drug.

Table 5. Analysis Windows for Safety Analysis for Period 1 (for Labs and Vital Signs)

Protocol Specified Visit Week	Lower Bound	Target Day	Upper Bound
Baseline	-99	1 ^a	1
2	2	15	22
4	23	29	43
8	44	57	71
12	72	85	min (99, first dose date of Period 2)

a. Day of first dose of study drug.

Table 6. Analysis Windows for Efficacy Analysis for Period 1 (for EQ-5D-5L, SF-36, FACIT-F and RA-WIS)

Protocol Specified Visit Week	Lower Bound	Target Day	Upper Bound

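### Creatinine Grade 1 as written counts any rise above the subject's own baseline, so the Grade 1 cell of the baseline-versus-maximum shift table would hold mostly within-subject variation

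*SAP*

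**What the plan says.** SAP 10.3.2.2 sets the scale for the laboratory shift tables: OMERACT grades in general, but "For creatine phosphokinase, creatinine, NCI CTC criteria will be used". In row L11 of SAP Appendix A, creatinine Grade 1 is "> 1 – 1.5 × Baseline; > ULN – 1.5 × ULN". The starred note at the end of Protocol Appendix N has the same rule: "Grade 1: > 1 – 1.5 × Baseline; > ULN – 1.5 × ULN". Neither document says whether the two limbs are alternatives or must both hold.

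Three cross-tabulations are planned by treatment group: "Category of the baseline value versus category of the final value", "Category of the baseline value versus maximum category" and "Category of the baseline value versus minimum category". No test is planned on them. SAP Table 5 gives laboratory data four post-baseline windows in Period 1: Weeks 2, 4, 8 and 12. Protocol 8.1.5.3 defines baseline as one value, the last non-missing one on or before the first dose.

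Two other analyses cover creatinine. SAP 10.3.2.1 compares mean change from baseline by visit with an ANOVA. SAP 10.3.2.3 counts potentially clinically significant values, which means Grade 3 or 4 only.

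**The concern.** A shift table is informative when the same rule grades both axes. Here it does not. A baseline value cannot exceed itself, so only the ULN limb can grade it. A later value is Grade 1 as soon as it is above baseline by the smallest reportable amount. Baseline-relative grading is not the difficulty in itself: haemoglobin (row K1) is also graded against the pre-treatment value, but its Grade 1 starts at a fall of 1.0 g/dL. Creatinine has no such margin, so ordinary variation between visits is enough.

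Protocol 6.1.1.3 lists "Increased serum creatinine and renal dysfunction" among the adverse events of special interest, so this table will be read. As specified, it would show a Grade 1 creatinine increase in most placebo subjects, and a reader could take that percentage for an incidence of renal toxicity.

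**Working it through.** **1. Which reading of the semicolon?** Test *and* on an example with assumed values: baseline 0.6, later value 1.2, ULN 1.0 mg/dL. The later value is 1.2/0.6 = 2.0 × baseline and 1.2/1.0 = 1.2 × ULN. Under *and* it is not Grade 1, because the baseline ratio is above 1.5. It is not Grade 2, because 1.2 × ULN is not above 1.5 × ULN. A doubling to above ULN would go ungraded. Under *and*, moreover, no baseline value could be Grade 1, 2 or 3. Only *or* gives a usable scale, and the steps below use it.

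**2. Exact rates with no drug effect.** The documents give no expected shift rate to reproduce. Take one baseline and k exchangeable post-baseline values without ties. The baseline is equally likely to hold any rank among the k + 1 values, so:

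- P(maximum > baseline) = k/(k + 1) = 4/5 = 80% for k = 4 (75% for k = 3)
- P(final > baseline) = 1/2 = 50%
- P(minimum > baseline) = 1/(k + 1) = 1/5 = 20%

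These need no assumption about the size of the variation.

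**3. Allowing for ties and the ULN.** The SAP asks for SI units but gives no reporting precision. Assumptions, none from the documents: mean 0.65 mg/dL, between-subject CV 18%, within-subject CV 4–10%, ULN 0.9 mg/dL. Simulation of 300,000 subjects per setting gives these shifts from Grade 0 to Grade 1 or higher among subjects with a normal baseline:

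| Reported to | Maximum | Final | Minimum |
|---|---|---|---|
| 0.001 mg/dL | 80–81% | 50–51% | 20–21% |
| 0.01 mg/dL or 1 µmol/L | 75–80% | 44–49% | 16–19% |
| 0.1 mg/dL | 31–58% | 15–31% | 4–9% |

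A separate run (between-subject CV 20%, within-subject CV 4–8%, ULN 1.0 mg/dL, same fine rounding) gives 15–18% in the minimum table. In the maximum table, 75–80% of 48 is about 36–38 subjects per group if all have a normal baseline (0.75 × 48 = 36; 0.80 × 48 = 38.4). Grade 2 or higher with no effect stays below 1%.

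**4. Does the cell still respond to a true effect?** With within-subject CV 6%, rounding to 0.01 mg/dL and 48 per arm, a true 5% rise moves the maximum table from 77% to 93% (nominal two-sided 5% power about 57%) and the final table from 47% to 69% (about 60%). For mean change at the final visit, the difference is 0.05 × 0.65 = 0.0325 mg/dL and the SD of change is √2 × 0.06 × 0.65 = 0.055. The standardised difference is 0.59, and 0.59 × √(48/2) − 1.96 = 0.93, so power is about 82%. A true 8% rise gives 97% in the maximum table (power 83%) and 80% in the final table (93%). The cell does respond, from a high floor and towards a ceiling.

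**5. Grade 1 on the ULN limb only.** With mean 0.6–0.7 mg/dL, between-subject CV 20%, within-subject CV 4–8% and ULN 1.0 mg/dL, the no-effect rate in the maximum table is 0.4–5%, rising to 1.2–9.6% with a true 5% rise. Nominal power for that rise at 48 per arm is roughly 6–13%, against 35–82% under the present rule with the same assumptions.

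**The case against.** The strongest reply has four parts.

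- **Placebo column.** The tables are descriptive and show combined placebo beside each dose, so the background is in plain view. This stands, and it is why the point is minor. It does not make the placebo percentage a meaningful incidence of creatinine increase.
- **Departure from the named scale.** Removing one limb of Grade 1 creates a hybrid, and the limb kept from Grade 2 upward still cannot apply to a baseline value. Both statements are true. The first calls for a footnote. The second matters little, since fewer than 1% of subjects reach Grade 2 without a drug effect.
- **Sensitivity.** The present rule separates arms better than the ULN-only rule (step 5). This stands as a real cost of the change.
- **Ambiguity.** The SAP does not state *or*. Under *and*, the no-effect shift in the maximum table would be only about 1–8%. But *and* breaks the scale (step 1), and a choice left to the programmer is itself a gap.

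A reader might infer more than the documents support. That the table cannot discriminate is wrong (step 4). That about three in four subjects shift in all three tables is wrong too; the figure belongs to the maximum table. Nor would the special-interest event counts be inflated: SAP Table 13 identifies renal dysfunction by a narrow MedDRA query, not by laboratory grade. Finally, the problem does not grow over the extension in any table the SAP specifies, because SAP 10.3.3 lists no long-term shift table.

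**Conclusion.** The concern holds in limited form. As written, the rule labels within-range variation as Grade 1 and grades the two axes differently. The 80% figure for the maximum table rests only on the *or* reading, four post-baseline values, exchangeability and no ties. The 75–80%, 44–49% and 15–19% ranges also rest on the assumed creatinine distribution and on reporting to about 0.01 mg/dL or 1 µmol/L. Reporting to 0.1 mg/dL would bring the maximum table down to 31–58%.

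The effect is confined to the Grade 1 cell of one analyte, where the absolute percentage would overstate creatinine increases in all arms. Severity is minor: nothing is tested on these tables, and the analyses that carry the creatinine comparison do not depend on the Grade 1 cut.

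**What to change.** In SAP Appendix A, row L11, and the starred note of Protocol Appendix N:

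1. State that the two limbs are alternatives (*or*).
2. For the shift tables, grade creatinine Grade 1 on the ULN limb only, for baseline and post-baseline values alike, and keep the baseline-relative limb from Grade 2 upward.
3. Footnote that this departs from NCI CTC Grade 1.

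Row L11 needs an edit anyway. It carries the footnote mark for the unit changes in L3, L7 and L8 rather than the mark for NCI CTC grading, and the single-star note describes an L11 cut that the row no longer contains.

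The cost is a line of wording and the grade derivation for one analyte. Rises of up to 1.5 × baseline within the normal range leave the shift table, which becomes less sensitive to small mean shifts. The mean-change ANOVA in SAP 10.3.2.1 assesses those. If the sponsor prefers to keep the NCI CTC grade intact, the minimum is to state *or* and note under the table that Grade 1 has a high background and that interpretation rests on Grade 2 or higher.
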